7 HANDLING OF MISSING VALUES

Where dates are ambiguous because of missing day and/or months, standard imputation will be applied: where day is missing the 15th of the month will be assumed; where both day and month are missing the 1st of July will be assumed unless data collected is in 2017 (year of initiation of IPP) in which case the 15th of August will be assumed (midpoint as IPP was initiated in April 2017). The 15th of August will only be used for missing dates that are related to the IPP program, e.g., start date of palbociclib cycle. Where other types of data are missing from the original medical record, the affected analyses will be conducted using only the results of those patients with data available and the number included in each analysis will be stated. The percentage of data missing will be reported for each study variable. The calculation of percentages will not contain the missing categories. Counts of missing observations will be presented in a separate category.

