Where dates are ambiguous because of missing day and/or months, standard imputation will be applied: where day is missing the 15th of the month will be assumed; where both day and month are missing the 1st of July will be assumed unless data collected is in 2017 (year of initiation of IPP) in which case the 15th of August will be assumed (midpoint as IPP was initiated in April 2017). Where other types of data are missing from the original medical record, the affected analyses will be conducted using only the results of those patients with data available and the number included in each analysis will be stated. The percentage of data missing will be reported for each study variable. The calculation of percentages will not contain the missing categories. Counts of missing observations will be presented in a separate category.

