2 INTRODUCTION

Note: in this document any text taken directly from the non-interventional (NI) study protocol is *italicised*.

Palbociclib was recommended for use with an aromatase inhibitor in patients with locally advanced and metastatic breast cancer (MBC) in the NHS in England by the National Institute for Health and Care Excellence (NICE) in November 2017 and by the Scottish Medicine Consortium (SMC) in December 2017^{1,2}. In order to provide access to palbociclib in the UK during the NICE/SMC appraisal period, the Ibrance® Patient Program (IPP) was run by Pfizer between April 2017 and November 2017 for England and Wales, and December 2017 for Scotland. The IPP provided free access to treatment to NHS patients with previously untreated (or >12 month since discontinuation of adjuvant or neoadjuvant treatment with a nonsteroidal aromatase inhibitor), Hormone Receptor Positive (HR+)/Human Epidermal Growth Factor 2 Negative (HER2-) MBC³.

Pfizer are interested in the opportunity to collect data from patients who received palbociclib as part of the IPP, to better understand effectiveness and safety of palbociclib when used in routine care in a UK context, with a focus on treatment persistence and dose management, patients' characteristics, clinical outcomes, and healthcare resource utilisation. This study will evaluate patients' clinical progression and experience of treatment with palbociclib in routine clinical practice in the UK. This study may be of benefit to the NHS and patients in supporting assessments of the benefit of palbociclib in routine care; and will also help contextualise evidence on safety of palbociclib previously generated from the real-world studies in US populations.

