2.1 STUDY DESIGN

This study will be a UK-wide, multi-centre, non-interventional cohort study (Figure 1). The study will involve secondary use of hospital medical records (paper-based or electronic, as appropriate), collected both retrospectively and prospectively, from patients' medical records. Data will be collected for a maximum of 3 years following enrolment into the IPP.

The palbociclib initiation date will be defined as the index date. The baseline period will extend from the date of diagnosis up to palbociclib initiation (index date). The post-initiation observation period will be defined as the period from the index date until the end of the 3-year follow-up period. Patients will contribute data up to the time that they are lost to follow-up (for example due to discharge, death, or other reasons) or 3-year post-index observation period, whichever is sooner.

PFIZER CONFIDENTIAL

[figure not shown]
[figure not shown]

Figure 1. Schematic of study design**Study population**

Across the entire UK, 846 women received palbociclib as part of the IPP. In the sites selected for this study, approximately 200 patients received palbociclib as part of the IPP and consented to participate in the study.

All patients meeting the following eligibility criteria will be included in the study:

- Patients enrolled into the IPP at one of the selected sites.
- Patients who received ≥ 1 dose of palbociclib as part of the IPP at one of the selected sites.
- For sites where data collection is performed by pH Associates, written informed consent will be required from living patients to access their medical records.
- Patient aged ≥ 18 years old at enrolment into the IPP

All eligible patients within the selected sites will be recruited into the study (and who provide informed consent, in the case of living patients, at sites where data collection is performed by pH Associates).

Data will be retrospectively collected from the point of patient's enrolment into the IPP until initial data collection, expected to take place between November 2018 and February 2019. After the initial retrospective data collection, data will be collected prospectively up to a maximum of 3 years from enrolment in the IPP by members of the direct care team by updating the eCRF with any subsequent therapeutic and progression data available in the medical records until the end of the 3-year follow-up period.

PFIZER CONFIDENTIAL

Data source

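### Partial dates are imputed to fixed calendar days without regard to known dates, so 2017 and index-month dates can fall on the wrong side of palbociclib start

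*SAP*

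**What the plan says.** Protocol 9.7 and SAP section 7 share one fixed-date rule. If only the day is unknown, "where day is missing the 15th of the month will be assumed". If only the year is known, "where both day and month are missing the 1st of July will be assumed unless data collected is in 2017". For 2017 the SAP continues: "in which case the 15th of August will be assumed (midpoint as IPP was initiated in April 2017".

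The SAP then adds a limit that the protocol lacks: "The 15th of August will only be used for missing dates that are related to the IPP program, e.g., start date of palbociclib cycle". By implication, other year-only 2017 dates fall back to 1 July. The protocol gives 15 August to every such date: "unless data collected is in 2017 (year of initiation of IPP) in which case the 15th of August will be assumed".

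Neither document bounds the imputed date by the patient's index, death or last-contact date, or says what to do with an impossible interval. The summary table in SAP 8.2.9 applies the rule to duration of metastatic disease, PFS, OS, time to best response and duration of response. The time origin is fixed in SAP 2.1: "The palbociclib initiation date will be defined as the index date". SAP section 2 gives the range of possible origins: the access programme (IPP) "was run by Pfizer between April 2017 and November 2017 for England and Wales, and December 2017 for Scotland".

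**The concern.** A fixed mid-period date is harmless when it is far from the time origin. Here the origin of every patient lies inside the year to which the special rule applies. A progression or response recorded only as 2017 may be set earlier than the first dose. A metastatic diagnosis or letrozole start recorded only as 2017 may be set later than it. With only the day missing, the same happens for any date in the index month.

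The results are negative times to progression or response and negative disease durations. What happens to them then depends on code that the plan does not describe. The rule also feeds a subgroup: SAP 5.4 separates patients whose letrozole was started more than 3 months before palbociclib, and SAP 8.2.9 reports nearly every outcome by treatment line.

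**Working it through.** **Inputs.** Imputation dates are from SAP section 7 and protocol 9.7. The IPP window is from SAP section 2. I take it as 1 April to 30 November 2017 (244 days), with 31 December (275 days) as the other end of the range. Assumption: index dates are spread evenly over the window; the documents do not give their distribution.

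**The plan's own figure.** The midpoint of 1 April and 31 December 2017 is 16 August, one day from the stated 15 August. With 1 April to 30 November it is 31 July, 15 days earlier. The stated midpoint therefore fits a window running to the end of 2017.

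**Worked patients under the written rule.**
- Index 20 September 2017, event recorded as 2017: 1 July minus 20 September = -81 days.
- Same index, event recorded as September 2017: 15 September minus 20 September = -5 days.
- Index 1 May 2017, metastatic diagnosis recorded as 2017: duration = 1 May minus 1 July = -61 days.

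**Share of index dates for which the order is wrong.** Share = index dates on the wrong side of the imputed date / days in the window.

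| Partial date | Set to | Window to 30 Nov | Window to 31 Dec |
|---|---|---|---|
| Post-index event, 2017 only | 1 July | 152/244 = 62% | 183/275 = 67% |
| Post-index event, 2017 only | 15 August | 107/244 = 44% | 138/275 = 50% |
| Baseline date, 2017 only | 1 July | 91/244 = 37% | 91/275 = 33% |
| Baseline date, 2017 only | 15 August | 136/244 = 56% | 136/275 = 49% |
| Post-index event in index month, day missing | 15th | 124/244 = 51% | 140/275 = 51% |
| Baseline date in index month, day missing | 15th | 112/244 = 46% | 126/275 = 46% |

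**Weighting by opportunity.** A late starter has little of 2017 left in which a post-index event can occur. Weight each index date by m, the days from index to 31 December inclusive.
- Window to 30 November: m runs from 275 down to 32, total 37,454. Index after 1 July: 16,340/37,454 = 44%. Index after 15 August: 9,095/37,454 = 24%.
- Window to 31 December: total 37,950. Index after 1 July: 16,836/37,950 = 44%. Index after 15 August: 9,591/37,950 = 25%.

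**Later years.** The earliest year-only date after 2017 is 1 July 2018, 182 days after the latest possible index date (31 December 2017). A day-missing date in January 2018 becomes 15 January, still after index. Dates from 2018 on therefore cannot precede index, but they can fall after a known death or last contact.

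**Letrozole subgroup.** If letrozole start is known only as 2017 and set to 1 July, the interval exceeds 3 months only for index from 2 October: 60/244 = 25% to 91/275 = 33% of index dates. If it is set to the midpoint of 1 January and index, the interval exceeds 3 months only for index after about 2 July. Either way the index date alone decides membership. For any index after 1 April, the true interval could lie on either side of 3 months.

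**The case against.** The best counter-argument is that incomplete dates should be rare. The dataset tables specify full day-month-year dates for everything but birth, and SAP section 6 takes progression from dated radiological assessments. A missing day moves a date by at most about 16 days, against the median PFS of 24.8 months that the protocol cites from the phase III first-line trial. A Kaplan-Meier median would barely move unless the record were dropped. This stands as a limit on the likely effect. It does not supply the missing bound.

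Safeguards exist: consistency checks in the eCRF (protocol 9.6) and programmed validation with queries (protocol 9.8). Reported ranges would also expose a negative duration. But the checks are described for entered data and are not stated to act on imputed dates. The SAP also describes disease duration with the subtraction in opposite directions (8.2.1 and 8.2.9), so a sign check is not dependable.

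Four stronger readings are tempting, and the documents do not support them.
- A reader might take 62-67% as a share of patients or events. It is a share of hypothetical index dates, for year-only 2017 events, under 1 July.
- A reader might infer that a reported time to toxicity is corrupted. Time to first neutropenia appears only under the proposed analyses in SAP 8.2.4; the actual analyses there are categorical.
- A reader might assume that software discards negative times. The documents do not say what happens to them.
- A reader might call the protocol-SAP difference on 15 August a breach. Protocol 9.7 lets the SAP modify the plan, and limiting an IPP midpoint to IPP dates is sensible. What remains is that IPP-related is illustrated by one example and not defined. The 2017 trigger must also mean the event year, since data collection began in November 2018 (protocol section 6).

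**Conclusion.** The point holds as a defect in a stated rule: followed as written, it can order dates impossibly in both directions. The exposure is confined to partial dates in 2017 or in the index month, and to later dates that overrun a known death or last contact.

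The misordering shares in the table and weighting above rest on evenly spread index dates. The weighted figures also assume that post-index events are equally likely on each remaining day of 2017. Reading the rule as 15 August reduces the problem for post-index events but does not remove it, and makes it worse for baseline dates. The documents do not say how many dates are partial, so no effect on median PFS, OS or response time can be calculated, and it may be small.

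**What to change.** In SAP section 7:

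1. Restrict each imputed date to its feasible window and use the midpoint. For post-index events, the window runs from the later of index and the start of the known period to the earliest of death, last contact and the end of the known period. For pre-index dates, use the part of the known period up to index.
2. List which 2017 dates count as IPP-related, and say that the trigger is the year of the event.
3. Report the number of imputed dates for each endpoint.
4. For the subgroup defined by more than 3 months of letrozole, do not let one imputed date decide. Class patients whose feasible window spans the 3-month cut as undetermined, or show the subgroup both ways. The midpoint in step 1 does not solve this case.

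For the worked patients, step 1 gives the following, taking no death or last contact before the end of the known period:
- Index 20 September, event 2017: window 20 September to 31 December (102 days), imputed 10 November, +51 days.
- Index 20 September, event September 2017: window 20 to 30 September, imputed 25 September, +5 days.
- Index 1 May, diagnosis 2017: window 1 January to 1 May (120 days), imputed 2 March, duration +60 days.

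The cost is a short SAP edit, a few lines of code and a rerun of the affected tables. The rerun is a real cost, because the SAP already reports many analyses as done. No new data are needed.

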8 STATISTICAL METHODOLOGY AND STATISTICAL ANALYSES

8.1 STATISTICAL METHODS

[figure not shown]
The following statistical methods will be used:

Full analysis will be conducted on 2-year follow up data not 3-year follow up data.

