5.1 FULL ANALYSIS SET

The full analysis set will be comprised of medical records extracted for the purpose of the study from all eligible patients who are enrolled into the study (either deceased with access to their medical records via their direct care team or living and having provided written informed consent to access of their medical records as part of the study). Analysis will be conducted on the 2-year follow-up data.

PFIZER CONFIDENTIAL

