 - Number of lines of prior chemotherapy for metastatic disease
 - Proportion of patients for whom an LHRH was used
 - Proportion of patients treated with endocrine therapy in the neoadjuvant or adjuvant setting
 - Endocrine therapy name
 - Proportion of patients treated with endocrine therapy in the advanced/disease modifying/metastatic setting
 - Endocrine therapy name
 - Number of lines of prior endocrine therapy for metastatic disease
- Proportion of patients treated with radiotherapy in the advanced/disease modifying/metastatic setting
- Concomitant medications (defined as medications prescribed whilst on palbociclib)
- Concomitant medications prescribed alongside goserelin

PFIZER CONFIDENTIAL

- Number of prior treatments in the metastatic setting, all prior therapies as well as chemotherapy/endocrine therapy combined and separately

[figure not shown]
Secondary Objective 1: To describe treatment pattern (as per licence/IPP requirement); including the proportion of patients with dose modification and who switch treatment 1, 2 and 3 years after palbociclib initiation, and median time to dose modification and treatment discontinuation ('drug survival'). For patients who progress, to describe the 1st /2nd /3rd line of treatment after progression.

- Summary measures of palbociclib treatment patterns including:
 - Starting Dose.
 - Endocrine partner prescribed alongside palbociclib
 - Proportion of patients with dose reductions at 1, 2 and 3 years after initiation.
 - Proportion of patients with palbociclib treatment discontinuation at 1, 2 and 3 years after initiation.
 - Reasons for discontinuation of palbociclib
 - Proportion of patients with temporary discontinuations
 - Time to dose reduction in number of days (from start of treatment) – 1st line treatment group only
 - Time to palbociclib discontinuation ('drug survival') in number of days (from start of treatment) in those patients permanently discontinuing palbociclib
 - Reasons for discontinuation.
 - 1st, 2nd, and 3rd line of treatment after progression: number of patients prescribed each medication, dose, and length of treatment.
- Description of the number of patients which are being prescribed as per posology of treatment.
 - Number of completed 28-day cycles per patient.
 - Proportion of patients co-administered letrozole at palbociclib initiation.
 - Proportion of patients co-administered fulvestrant at palbociclib initiation.

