- Summary measures of bone profile in the first 6 months following initiation:
 - Calcium.
 - Phosphate.
- Summary measures of urea and electrolytes in the first 6 months following initiation:
 - Creatinine
 - Potassium
 - Sodium
 - Urea
- Summary measures of radiological indicators in the first 6 months following initiation including the proportion of patients with:
 - Stable disease.
 - Progressive disease.
 - CR or PR.

Secondary Objective 6: To describe BC-related healthcare resource utilisation during the first year following palbociclib initiation.

- Summary measures of hospital admissions for each line of therapy, including:
 - Proportion of patients with at least one inpatient admission recorded
 - Inpatient admissions per patient.
 - Elective or non-elective.
 - Reasons for admission (including day cases).
 - Length of stay per inpatient admission.
 - Proportion of patients with at least one outpatient visit recorded
 - Outpatient visits per patient.
 - Reason for outpatient visit
 - Type of HCP seen during outpatient visits
- Proportion of patients with at least one interaction with CNS
- Number of CNS interactions per patient
- Type of CNS interaction
- Reason for CNS interaction
- Proportion of patients with at least one interaction with AOS
- Number of AOS interactions per patient
- Type of AOS interaction
- Reason for AOS interaction

For the estimation of endpoints, *the following definitions will be implemented. PFS will be defined as the time from the date of palbociclib initiation to the date of first documented disease progression (as documented in the radiological assessment section of the eCRF) or death. OS will be defined as the time from the date of palbociclib initiation until death from any cause. Time to achieving best overall response will be defined in patients who respond to treatment as the time from the date of palbociclib initiation until*

PFIZER CONFIDENTIAL

achievement of the best overall response: CR, or PR if CR is not achieved during follow-up. Duration of response will be defined as the time from the date CR or PR was first documented (whichever is recorded first) to the date of first documented disease progression or death from any cause (whichever occurs first).

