8.2 STATISTICAL ANALYSES

Definitions will be implemented as in section 8.1.3. Patients who are known to be alive at the date of data collection (1-year for interim report and 3-year for full study report) will be censored at the date of data collection, and patients who are lost to follow-up will be censored on the date they were last known to be alive (e.g., date of last recorded hospital visit). Patients who are alive and free from disease progression at the date of data collection and those lost to follow-up will be censored on the date they were last known not to have disease progression (i.e., the date of last documented response assessment). Patients remaining in CR or PR at the end of the post-initiation observation period or lost to follow-up will be censored on the date CR or PR was last documented.

[figure not shown]
[figure not shown]
Note: Some analyses that were originally proposed were not conducted as per the decisions of the CI and Pfizer team, these have been kept in this section as a record.

8.2.1 Primary Objective: To describe patient demographic and clinical characteristics at initiation of palbociclib.

Proposed: Age, duration of MBC prior to palbociclib (calculated by subtracting the date of initial BC diagnosis from the date of palbociclib initiation), number of lymph nodes involved, tumour size at initial disease diagnosis and Ki67 values will be summarised as quantitative variables (see section 8.1.1) using measures of central tendency (mean and median) and dispersion (standard deviation, interquartile range [IQR] and range) will be calculated. All other variables analysed as part of the primary endpoint, whether categorical or binary, will be presented as frequencies and percentages.

Actual: Age was presented as both a quantitative variable as per section 8.1.1 and as a categorical variable (Categories: Less than 40 years old, between 40 and 50 years old,

PFIZER CONFIDENTIAL

[figure not shown]

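### The SAP moves the full analysis to 2-year data without defining the cut and leaves 3-year rules in force; Kaplan-Meier PFS near month 24 could depend on which cut is meant

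*SAP*

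**What the plan says.** The move to two years is stated twice: "Full analysis will be conducted on 2-year follow up data not 3-year follow up data" (SAP 8.1) and "Analysis will be conducted on the 2-year follow-up data" (SAP 5.1). The research question in SAP 2.2, the time point for PFS, OS and response in SAP 6, and the headings of SAP 8.2.2 and 8.2.3 were changed to match.

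Other text in force was not changed:

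- **Overall survival censoring (SAP 8.2).** Living patients "1-year for interim report and 3-year for full study report) will be censored at the date of data collection". This paragraph stands above the note that superseded proposals are kept as a record.
- **Responder censoring (SAP 8.2).** "Patients remaining in CR or PR at the end of the post-initiation observation period or lost to follow-up will be censored" at the last documented response. SAP 2.1 defines the period it relies on: "The post-initiation observation period will be defined as the period from the index date until the end of the 3-year follow-up period".
- **Endpoints (SAP 6, Secondary Objective 1).** The list, introduced as reflecting the analyses conducted, includes "Proportion of patients with palbociclib treatment discontinuation at 1, 2 and 3 years after initiation" and the matching dose-reduction item. SAP 8.2.2 computes both at 1 and 2 years only.
- **Summary table (SAP 8.2.9).** One treatment-pattern row title still names years 1, 2 and 3.

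Two further rules make the cut matter for PFS. Progression is dated "as documented in the radiological assessment section of the eCRF" (SAP 6). Patients alive and progression-free are "censored on the date they were last known not to have disease progression (i.e., the date of last documented response assessment") (SAP 8.2).

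**The concern.** A programmer cannot tell from this text where follow-up ends. Truncation at 24 months from each index date and a collection held once the last starter reached 24 months are both natural readings. OS up to month 24 is the same under either. The OS curve beyond month 24, the length of follow-up (listed in SAP 6), and the end of the PFS curve are not.

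PFS is the sensitive one. Under a common cut at month 24, each patient's last usable assessment falls before month 24. Progression-free patients leave the risk set there, while progressions found at those same assessments still count as events. The late events are divided by a shrinking number at risk, so the curve drops and becomes erratic just where it is read. In a descriptive study the estimate is itself the result.

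**Working it through.** The study is descriptive and states no power or event figure to reproduce. The check has four parts.

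**1. Do the planned dates settle the cut?** The IPP ran from April to December 2017 (SAP 2). Protocol 6 ends retrospective collection in February 2019 and prospective collection in February 2021.

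- Starts on 1 April and 31 December 2017 are 22 and 13 months before 1 February 2019.
- They are 46 and 37 months before 1 February 2021.

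Neither is a 2-year date.

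**2. Does the cycle category settle it?** The top completed-cycle category in SAP 8.2.2 is 25-27. Two years hold 730.5 / 28 = 26.1 cycles. Twenty-seven cycles need 27 × 28 = 756 days, or 756 / 30.44 = 24.84 months. This suggests follow-up somewhat beyond 24.0 months. It does not prove it, and it fits a long collection wave poorly too: 32 months would hold 34 complete cycles.

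**3. Size under a strict 24.0-month cut, by hand.** Inputs: n = 200 (SAP 2.1); median PFS 24.8 months (a first-line reference in Protocol 7). Assumed: exponential PFS, 3-monthly assessments at random phase, 10% loss by month 24.

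- True 24-month PFS: 2^(−24/24.8) = 51.1%.
- Dating progression at the next assessment adds 1.5 months on average. Documented PFS is therefore about 2^(−19.5/24.8) = 58.0% at month 21 and 2^(−22.5/24.8) = 53.3% at month 24.
- At risk at month 21: 200 × 0.580 × 0.9^(21/24) ≈ 106.
- Each of these has one assessment left, which shows progression with probability p = 1 − 2^(−3/24.8) = 0.0804. All leave in turn, so the expected Kaplan-Meier factor for the last interval is ∏(1 − 0.0804/k), k = 1 to 106, which is 0.652.
- Strict-cut estimate: 0.580 × 0.652 = 37.8%. With follow-up continuing, the factor is 1 − p = 0.920 and the estimate is 0.580 × 0.920 = 53.3%.

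**4. Simulation of the SAP's censoring rule.** Same inputs, 600 samples per setting. The wave is administrative censoring uniform on 24 to 32 months, an assumption (uniform April to December 2017 starts, cut when the last starter reaches 24 months). Entries are mean 24-month Kaplan-Meier PFS, %.

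| Median; assessments | Cut 24.0 | Cut 24.84 | Wave | 36 months |
|---|---|---|---|---|
| 24.8; 3-monthly, SD 2 weeks | 37.8 | 52.4 | 53.0 | 53.3 |
| 24.8; 3-monthly, random phase | 38.1 | 51.0 | 53.0 | 53.3 |
| 24.8; 6-monthly, SD 2 weeks | 27.2 | 53.8 | 54.4 | 55.6 |
| 24.8; 6-monthly, random phase | 27.2 | 46.4 | 53.8 | 55.3 |
| 20.2; 3-monthly, SD 2 weeks | 30.4 | 45.2 | 45.9 | 46.2 |
| 15; 3-monthly, SD 2 weeks | 20.7 | 34.5 | 35.1 | 35.4 |
| 24.8; 3-monthly, all exactly on schedule | 51.0 | 51.0 | 51.0 | 51.0 |

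Repeat runs of the first row gave 36 to 38% at the strict cut. In that row the typical number at risk at month 24 is 0 (strict), 46 (24.84 months) and 76 (wave). The SD of the estimate is about 14 points at the strict cut and about 4 for the others.

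Median PFS at a true 24.8 months, 3-monthly: 23.4 to 23.7 months at the strict cut where reached (not reached in 16% of samples), against 26.2 to 26.7 with 36 months. At 24.84 months it is still about 24.2, because the true median lies at the cut. At a true 20.2 months the cut hardly matters (21.2 v 21.3), and at 15 months not at all (16.0 under each).

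**The case against.** The strongest reply has four parts.

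- **The override is explicit.** SAP 8.1 says 2-year, not 3-year, and much of the remaining 3-year wording repeats the protocol. This stands to the extent that nobody should think a 3-year analysis is intended. But the override does not say what the 2-year cut is, and the surviving rules are the only censoring rules given.
- **The large gap needs a cut at exactly 24.0 months.** This stands. The cycle category points to somewhat longer follow-up, and a cut at 24.84 months recovers 24-month PFS in most settings; fully random 6-monthly timing (46.4%) is the exception. The documents give no assessment schedule, so timing is assumed throughout.
- **The SAP does not commit to Kaplan-Meier proportions.** SAP 8.2.9 plans frequency tables for the 2-year proportions, and SAP 8.1.3 makes Kaplan-Meier optional for them. This stands for the 24-month figure. Median PFS is committed to Kaplan-Meier and can also be affected.
- **Collection dates are in the eCRF** (SAP 11). So the OS rule is stale rather than unusable, and no patient is carried past last contact.

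A reader might infer that the study's 24-month PFS is too low by 15 points or more. The documents do not support that: they do not establish a strict 24.0-month cut, and a display of numbers at risk would expose an empty risk set. Nor can one give a direction of bias for the plain percentages. SAP 8.2.9 excludes missing patients, but the only stated denominator (SAP 8.2.3) is patients known to be alive, which would tend to push PFS upward.

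**Conclusion.** The inconsistency is established from the text: the 2-year cut is undefined, the censoring rule and observation period still say three years, and two listed 3-year proportions cannot come from 2-year data.

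The numerical consequence is conditional. With a cut at exactly 24.0 months, irregular assessments and a 24.8-month median, 24-month Kaplan-Meier PFS averages about 37 to 38% instead of 53%, and the median where reached is about 23.5 instead of 26.5 months. The 24-month gap vanishes if everyone is assessed at month 24 and is mostly gone with about 25 months of follow-up. The median shift fades if the true median is well below 24 months. These sizes rest on assumed exponential PFS, assessment timing and 10% loss. The SAP should be corrected because it does not tell the reader which case applies.

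**What to change.** 1. State one cut-off, either 24 months from index or a dated collection, and make the SAP 8.2 censoring rules and the SAP 2.1 observation period match it. For PFS, use response assessments recorded after month 24 where they exist, so that the 24-month estimate does not rest on an empty risk set.
2. Remove the 3-year proportions from SAP 6 (Secondary Objective 1) and correct the row title in SAP 8.2.9, or mark them as not analysed. Leave the Proposed paragraph in SAP 8.2.3 as the record it is meant to be.
3. Report 2-year PFS and OS as Kaplan-Meier estimates with 95% confidence intervals and numbers at risk, in place of the plain percentages in SAP 8.2.9 and the optional wording in SAP 8.1.3. Give medians or limits as not reached where that is so.

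Reading PFS at 12 or 18 months as well is optional and should be labelled post hoc, since SAP 8.2.3 records a decision for the 2-year time point only.

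Cost: SAP rewording and a few Kaplan-Meier read-outs from data already collected. The downside is uneven follow-up beyond month 24 if a dated collection is chosen, which the numbers at risk will show.
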